8.2.7 Premature Withdrawal / Early Termination Visit

All attempts should be made to perform all the tests for Day 28 at the Withdrawal/Early Termination visit for patients who may withdraw consent for further participation in the study before completion.

8.2.8 Unscheduled Visits

If a patient returns to the site prior to their next scheduled study visit for assessment of an adverse event (*e.g.*, before Day 28), or at the request of the Investigator, the Unscheduled Visit forms of the eCRF should be completed. Procedures and examinations conducted at the Unscheduled Visit

are at the discretion of the Investigator. If the patient withdraws consent for further participation at the Unscheduled Visit, the eCRF forms for the Premature Withdrawal / Early Termination Visit, and the End of Study Form should be completed rather than the Unscheduled Visit form.

8.2.9 Appropriateness of Measurements

Prevention of ARDS will reduce morbidity and mortality in infected patients, amongst others.

8.2.10 Data Quality Assurance

Steps to be taken to assure the accuracy and reliability of data include the selection of qualified PIs and appropriate study centers, review of protocol procedures with the PI and associated personnel prior to the study, and periodic monitoring and site audits by the Sponsor or their designee. The data will be entered into the clinical trial database and verified for accuracy.

9 STATISTICAL METHODS PLANNED AND SAMPLE SIZE

9.1 Determination of Sample Size

The sample size (n=60) was determined based on medical judgement and a desire to assess safety in a limited number of patients, prior to further study and patient availability: 30 patients (active) and 30 patients (placebo).

9.2 Patient Populations

9.2.1 Full Analysis Set (FAS)

The Full Analysis Set is defined as patients who received any amount of at least one dose of study medication, with assignment to treatment as randomized.

9.2.2 Per Protocol (PP) Population

The Per Protocol population is defined as patients who meet all inclusion/exclusion criteria, were within the acceptable compliance range ($\geq 80\%$ and $\leq 120\%$), and completed the study with no major protocol violations. The Per Protocol population will be finalized prior to breaking the blind for final reporting.

9.2.3 Safety Population

The safety population is defined as all patients who received at least one dose (partial or complete) of the study medication, assigned to treatment according to the treatment actually received.

9.3 Statistical Methods

In general, continuous variables will be summarized with descriptive statistics (the number of non-missing values [n], mean, median, standard deviation [SD], minimum, and maximum). All categorical variables will be summarized with frequency counts and percentages, as applicable.

A detailed statistical analysis plan (SAP) will be developed which will describe all analyses to be performed. The SAP will be finalized prior to database lock and unblinding.

9.3.1 Demographic, Medical, and Disease History

All baseline characteristics, demographics, and medical history (by body system) will be summarized by treatment within each age cohort as well as overall. For continuous variables, n, mean, standard deviation, median, minimum, and maximum will be presented. For categorical variables, frequency counts and percentages will be presented. No formal statistical analysis methods will be employed.

Summary and/or data listings of the prior, concomitant medications, in particular AEDs, and class of medication will be provided.

9.3.2 Efficacy Analyses

The primary efficacy endpoint is the proportion of subjects alive and free of respiratory failure (*e.g.*, need for non-invasive or invasive mechanical ventilation, high flow oxygen (≥ 6 L/minute), or ECMO) and free of the need for continued renal replacement therapy (RRT) on Day 28. The need for continued RRT at Day 28 will be defined as either dialysis in the past 3 days (Day 26, 27, or 28) or an eGFR on Day 28 <10 mL/min/1.73 m².

Analyses for the primary and the key secondary endpoints will be performed on the FAS and PP populations, with the analysis on the FAS as the primary analysis; all other efficacy endpoints will be analyzed on the FAS population only.

Time to event variables will be summarized using Kaplan-Meier survival curves and compared between treatment groups using either Log-rank tests or Cox's Proportional Hazard model adjusting for baseline covariates, as necessary. For continuous variables assessed at multiple time points a Mixed Model Repeated Measures (MMRM) approach will be used or Analysis of Covariance (ANCOVA) if assessed at a single time point post-baseline. For categorical endpoints Cochran-Mantel-Haenszel (CMH) methods will be used, or a logistic regression approach, in the case of continuous covariates.

Additional details regarding precise endpoint definitions (including transformations, as applicable), analysis model specifications and alpha-level control for primary and important secondary endpoints associated with multiplicity will be provided in the SAP, to be finalized prior to unblinding the study.

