4.2.2 Secondary Efficacy Endpoints

Secondary efficacy endpoints include:

- All-cause mortality
- The presence and severity of ADRS as an ordinal outcome of the proportion of patients who have none, mild, moderate, or severe ARDS
- Time to each of mild, moderate, and severe ARDS
- The number of ventilation-free days and ECMO-free days
- Time on nasal canula or oxygen mask
- Length of stay in ICU and hospital (admission to discharge)
- Virologic clearance rate
- Worst PaO₂/FiO₂ ratio following enrollment
- Change in PaO₂/FiO₂ ratio
- Vasopressor-free days
- Change from maximal radiographic damage to EOT
- Change in baseline mMRC score

- Change in APACHE II score
- Proportion of patients with extrapulmonary organ dysfunction using the daily SOFA score
- Change in liver function tests (ALT, AST, total bilirubin)
- Change in renal function tests (SCr, eGFR)
- Change in hs-troponin levels
- Change in ACT, aPTT, and/or PT/INR values
- Change in antiviral IgG, IgA, and IgM levels.

4.2.3 Health Outcomes endpoint:

- Total healthcare costs from admission to discharge between treatment groups.

4.2.4 Exploratory Endpoints:

- Change in serum cytokines including IL-1 α , IL-1 β , and ferritin levels, as well as other exploratory biomarkers drawn at the same time as LSALT peptide concentrations.
- Change in baseline antiviral immunoglobulins (IgG, IgM, IgA) at EOS.

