Duration of therapy will be a maximum of 14 days. Patients will be maintained on the standard of care (SOC) for the treatment of COVID-19 as defined by institutional guidelines and/or physician practice. Co-morbidities and concomitant medications will be reviewed daily and documented in the patient's eCRF. The risk of venous thromboembolism (VTE), a potential consequence of SARS-CoV-2 infection, will be assessed and prophylaxis will be included as SOC for every patient (Zhai et al, 2020; Klok et al, 2020). Please refer to antithrombotic therapy in patients with COVID-19 (COVID-19 Treatment Guidelines Panel, Antithrombotic Therapy in Patients with COVID-19, p197; 17-December-2020).

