5.3 Discussion of Study Design

This double-blind, placebo-controlled, proof-of-concept Phase 2 study is designed to evaluate LSALT peptide compared with placebo in a defined number of adult hospitalized patients with the diagnosis of COVID-19. This is a 1:1 randomization comparing 5 mg LSALT peptide daily with matching placebo. LSALT peptide or drug-free saline will begin immediately once the patient meets all inclusion/exclusion criteria at the start of hospitalization and followed with physical and respiratory exams, blood chemistries, coagulation, hematology, ECGs, SARS-CoV-2 tests, CXRs, biomarkers, and PK will be recorded periodically throughout the 28 day study. When clinically indicated, questionnaires (APACHE II, SOFA) will be obtained at Baseline, EOT, and EOS; venous blood gas (VBG) or HCO_3 (bicarbonate) levels may be substituted for arterial blood gas (ABG) if it is SOC or in the patient's best interest, and results in comparable APACHE II and SOFA scores (Brown *et al*, 2016). Other questionnaires (Berlin Definition and modified Medical Research Council Dyspnea Scale) will be assessed at Baseline, Day 3, EOT, and EOS. Patients will be maintained on SOC, including prophylaxis or treatment for VTE, per institutional guidelines throughout the study. Dosing will end on Day 14, or at cure or increasing severity of ARDS, or at death. Patients will be followed clinically, and safety and efficacy measures will be recorded at end of study (EOS; Day 28) or death, whichever occurs first.

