7.3.2 Other Assessments

7.3.2.1 Clinical Laboratory Tests (Appendix 2)

- Hematology Complete blood count: total white blood cell count with differential (neutrophils, lymphocytes, monocytes, eosinophils, and basophils), total red blood cells (RBC, hemoglobin [Hgb], hematocrit, mean corpuscular volume, mean corpuscular Hgb, and mean corpuscular Hgb concentration), and platelets.
- Biochemistry Sodium, potassium, glucose, blood urea nitrogen, chloride, creatinine and eGFR, calcium, bilirubin (total), alkaline phosphatase, aspartate transaminase, alanine

transaminase, gamma-glutamyl transferase, total protein, albumin, and carbon dioxide (CO₂).

- Coagulation Activated Partial Thromboplastin Time (aPTT), Prothrombin time (PT), International Normalized Ratio (INR), and activated clotting (or coagulation) time (ACT), the latter only if part of SOC at the investigational site.
- Urinalysis Dipstick for presence of blood, glucose, ketones, and protein; pH, color (if applicable), transparency, specific gravity, and urobilinogen.

Blood and urine samples will be obtained at Screening, and prior to the drug infusion on Days 3, EOT, and at EOS, and as clinically indicated for evaluation of blood chemistries, hematology, coagulation, and urinalysis.

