8 STUDY PROCEDURES AND FLOW CHART

8.1 Study Flow Chart

Calendar	Admission ^a	Admission ^b	Treatment Period	Treatment Period	EOT	EOS
Day	1	1	1 – 14 (max)	3	Variable	28±3
Sign informed consent	X					
Assign screening number	X					
Inclusion/exclusion criteria	X					
Review demographics	X					
Review medical history	X					
Concomitant meds ^c	X		X	X	X	X
Physical exam ^c	X		X	X	X	X
Respiratory exam ^c	X		X	X	X	X
Urine pregnancy in WCBP	X					
Clinical labs/Urine tests ^{c,d}	X			X	X	X
12-lead ECG ^e	X			X	X	X
Vital signs ^{c,f}	X		X	X	X	X
eGFR ^{b,d}	X			X	X	X
SARS-CoV-2 testing swabs ^{c,g}	X			X	X	X
Chest x-ray ^h		X		X	X	X
PK and biomarker samples ⁱ		X		X	X	X
Randomization		X				
Study drug administration		X	X	X	X	X
AE assessments		X	X	X	X	X
SARS-CoV-2 IgG, IgA, IgM levels		X				X
Berlin Definition ^{j,k}		X		X	X	X
SOFA score ^{j,l}		X		X	X	X
mMRC score ^{j,m}		X		X	X	X
APACHE II score ^{j,n}		X		X	X	X
Health Outcomes						X

^a Screening to determine eligibility (prior to randomization)

^b Baseline after Screening and prior to the start of study drug unless otherwise indicated.

^c Performed at Screening, Day 3, and EOT prior to drug administration, and at EOS.

^d Hematology, biochemistry, coagulation, and urinalysis will be obtained and eGFR will be calculated (Appendix 2), and when clinically indicated.

^e 12-Lead ECG (supine) will be recorded at time 0 (pre-dose) at Screening, Day 3, EOT, and at EOS (only if clinically indicated). Also, an ECG will be obtained during the study when clinically indicated.

^f Blood pressure (supine), pulse rate (supine), body temperature, respiration rate (supine), actual body weight (kg), and height (cm). Note: Height will only be measured at Screening.

^g Swabs (nasal, throat, sputum, or lower respiratory tract) at Screening, Day 3, EOT, and EOS.

^h Chest x-rays at Baseline (Day 1), Day 3, at time of clinical improvement, at EOT, and EOS. A chest x-ray will also be obtained if clinically warranted and recorded in the eCRF.

ⁱ Blood draws at Baseline pre-dose, at the mid-point (1 hr) and at the end of 2-hr infusion of study drug on Days 1, 3, and EOT, and a single blood draw at EOS.

^j Obtained at Baseline, Day 3, when clinically indicated, at EOT, and at EOS.

^k Appendix 3

^l Appendix 4

^m Appendix 5

ⁿ Appendix 6

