8.2.5 End of Treatment (EOT)

The EOT visit refers to the completion of the last dose of study drug. All study assessments outlined during the Treatment Period are to be performed. For a complete list of assessments, refer to the Study Flow Chart.

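### The radiographic endpoint runs from a post-randomisation worst film to a course-dependent EOT, so preventing damage can count against the drug; the MMRM time variable should be set to fixed days

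*Combined protocol and SAP*

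**What the plan says.** **Radiographic endpoint.** Sections 4.2.2 and 7.1.2 list "Change from maximal radiographic damage to EOT" as a secondary efficacy endpoint. Section 7.3.2.5 and the flow chart (8.1) schedule films at Baseline, Day 3, EOT and EOS. Further films are taken at clinical improvement and when clinically indicated. Neither the assessment section nor the appendices name a film score.

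**When EOT falls.** The flow chart gives its day as variable. Section 8.2.5 says: "The EOT visit refers to the completion of the last dose of study drug". Section 5.1 sets only a ceiling: "Duration of therapy will be a maximum of 14 days". Section 5.3 adds triggers linked to the patient's course: "Dosing will end on Day 14, or at cure or increasing severity of ARDS, or at death". The discontinuation lists in the synopsis and section 5.4.3 name neither cure nor increasing ARDS severity.

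**Continuous endpoints.** Section 9.3.2 states: "For continuous variables assessed at multiple time points a Mixed Model Repeated Measures (MMRM) approach will be used". The scores are "Obtained at Baseline, Day 3, when clinically indicated, at EOT, and at EOS". For laboratory tests, "Blood and urine samples will be obtained at Screening, and prior to the drug infusion on Days 3, EOT, and at EOS". EOT is therefore the only scheduled score and laboratory point between Day 3 and Day 28. Section 9.3.2 also says that "analysis model specifications and alpha-level control for primary and important secondary endpoints associated with multiplicity will be provided in the SAP", and section 9.3.7 defers intercurrent events to the SAP. That SAP is not in the documents provided.

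**The concern.** The trial aims to prevent lung and kidney injury. An endpoint that starts from each patient's worst film gives credit for recovering from damage and none for avoiding it. A patient who never worsens has little to improve from; a patient who worsens badly and then clears scores a large improvement. Treatment can change the starting value, so randomisation does not balance it.

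The set of films from which the worst is taken also depends on the patient's course, because extra films follow clinical events. The end point is not a common time either: under section 5.3 the patient's course can set the day of EOT.

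The MMRM raises a related but weaker question. If EOT becomes a nominal visit level, the arms are compared there at different times since randomisation whenever treatment changes how long dosing lasts.

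**Working it through.** The documents give no effect size or SD for these endpoints, so there is no planned figure to reproduce.

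**1. Radiographic endpoint**

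Let B be the baseline film, M the maximum and E the EOT film, with higher values meaning more damage. Improvement from maximum is

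M − E = (M − B) + (B − E).

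The first bracket is post-randomisation worsening, entered as if it were benefit.

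Assumptions:
- The baseline film counts towards the maximum.
- Every patient would improve by g by EOT without worsening, and g is equal in both arms.
- A share w worsens by r points, and a fraction k of that rise remains at EOT.

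Then:
- Non-worsener: M − E = g; B − E = g.
- Worsener: M − E = g + r(1 − k); B − E = g − kr.

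With d = w(placebo) − w(active), the active-minus-placebo differences in mean improvement are:
- from maximum: −d × r × (1 − k)
- from baseline, to a film on the same day: +d × k × r

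Section 9.3.6.1 gives 28% and 22.4% as unfavourable-outcome rates for the primary endpoint. Borrowing them as the share whose film worsens is an assumption: d = 0.28 − 0.224 = 0.056. Complete prevention would give d = 0.28.

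| State of the rise at EOT | From maximum | From baseline |
|---|---|---|
| Fully resolved (k = 0) | −0.056r | 0 |
| Half resolved (k = 0.5) | −0.028r | +0.028r |
| None resolved (k = 1) | 0 | +0.056r |
| EOT film at the peak (E = M) | +0.056g | +0.056(r + g) |

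For r = 1, 2 and 4 points the first row gives −0.056, −0.112 and −0.224. With complete prevention it gives −0.28, −0.56 and −1.12. A negative value favours placebo, although the active arm had less damage.

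The last row applies if worsening itself ends dosing, as section 5.3 allows. There k = 1 + g/r, and the sign turns. The direction thus depends on a rule that sections 5.3 and 5.4.3 state differently. Change from baseline is never reversed in this model.

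**2. EOT as an MMRM visit**

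First model (all inputs assumed): a 10-point score falls linearly to 0 at recovery; recovery time is lognormal with log-SD 0.4, clipped to 3–40 days; EOT = min(recovery, 14). Arm differences (active minus placebo; lower is better):

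| Median recovery, placebo vs active (days) | Day 7 | EOT | Fixed Day 14 | Day 28 |
|---|---|---|---|---|
| 10 vs 7 | −1.65 | −0.313 | −0.313 | −0.005 |
| 12 vs 9 | −1.50 | −0.539 | −0.539 | −0.019 |
| 8 vs 6 | −1.05 | −0.106 | −0.106 | −0.001 |

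EOT and Day 14 agree by construction: a patient recovered before Day 14 scores 0 on both, and for the others EOT is Day 14.

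Second model (log-SD 0.5, fall from a mean of 8 to a cure level of 2, noise SD 1.5), median 9 vs 6 days: Day 7 −1.21, EOT −0.35, Day 14 −0.38, Day 28 −0.02. Mean EOT day is 9.7 vs 7.1, so the arms are measured 2.6 days apart. With no treatment effect the EOT difference is 0. If the drug only prevents worsening (28% to 22.4%), EOT gives −0.58 and Day 7 gives −0.47, so there is no attenuation.

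**The case against.** The best defence is that nothing in the protocol makes EOT an MMRM visit level. Model specification, precise endpoint definitions and intercurrent events are all left to the SAP. That stands: for the MMRM this is an open item and not an error. It does not cover the radiographic endpoint, whose start and end are written into its name.

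A reader might compare Day 7 with EOT in the first model and infer that the variable visit hides most of a faster recovery (1 − 0.313/1.65 = 0.81). The figures do not support this. EOT equals a fixed Day 14 in that model, so the loss is the gap between Day 7 and Day 14, by when most patients have recovered. No score or laboratory value is scheduled on Day 7.

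A reader might also infer that a Day 28 contrast would recover a speed effect. It would not: Day 28 retains 0.001 to 0.019 points in the first model.

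It is also fair to say that speed of recovery is already measured by ventilation-free days, time on oxygen and length of stay, and that this is one of many secondary endpoints.

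Finally, the reversal on the radiographic endpoint is not certain. It needs worsening that partly resolves before EOT. That limits the claim to one of possible direction; it does not make the endpoint interpretable.

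**Conclusion.** The point holds for the radiographic endpoint. It starts from a value that treatment can change, drawn from a course-dependent set of films, and ends on a variable day. When prevented worsening would have partly resolved by EOT, it favours placebo by d × r × (1 − k): 0.056 points per point of rise at full resolution under the borrowed 28% and 22.4%, and up to 0.28 with complete prevention. The size is illustrative, since the share who worsen, the rise and its resolution are all assumed and no film score is named. That the maximum is a post-randomisation starting point needs none of these assumptions.

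For the MMRM, the finding is only that the time variable is open and EOT is a likely level. The models show no spurious effect when there is none, and no attenuation when the drug only prevents worsening. The primary Day 28 endpoint, Day 3 contrasts and day-count endpoints are unaffected.

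**What to change.** Before unblinding:

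- **Radiographic endpoint:** define it as change from the baseline film to the Day 28 film, with change to Day 3 shown as well. Name the film score, and state how deaths enter, in line with the worst-outcome principle of section 9.3.7. Report maximum-to-EOT descriptively.
- **MMRM:** state in the SAP that treatment contrasts are at fixed study days (Day 3 and Day 28). Summarise EOT values descriptively with their actual study day.
- **End of dosing:** reconcile the triggers in section 5.3 with the discontinuation lists in the synopsis and section 5.4.3, since they determine what an EOT value means.

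The cost is mainly wording. The Baseline, Day 3 and Day 28 films are already scheduled, and section 9.3.4.3 already summarises chest x-ray changes from baseline. The downside is that Day 28 shows little of a pure speed effect, and a transient worsening that has cleared by then will not appear. Ventilation-free days, time on oxygen and length of stay remain the endpoints for speed of recovery.

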9.3.3 Pharmacokinetic Analysis

All plasma concentration data will be summarized using N, mean, SD, % coefficient of variation, median, minimum, and maximum by treatment and cohort. Attempts will be made to correlate LSALT peptide concentrations with cytokine levels.

9.3.4 Safety Analysis

9.3.4.1 Adverse Events

All safety analyses will be conducted on all patients who are in the Safety Population. AEs will be coded to system organ class and preferred term using MedDRA version 20.0 or higher. All AEs occurring after the initiation of the study treatment (TEAEs) will be collected, including events present at baseline that worsened during the study.

AEs will be summarized by treatment group to provide comparison among the treatment groups with respect to incidence of AEs (the number of patients reporting at least one episode of a specific AE), incidence of AEs by severity within body system, incidence of AEs by attribution within body system, and incidence of AEs causing withdrawal and incidence of SAEs. Regarding severity and attribution summaries, the most extreme outcome (highest severity and closest to study drug related) will be used for those patients who experience the same AE on more than one occasion.

Written narratives will be provided for all serious, unexpected, or other significant AEs that are judged to be of special interest because of their clinical importance.

9.3.4.2 Clinical Laboratory

Clinical Laboratory examination will be performed prior to treatment and during treatment.

Descriptive statistics will be presented for the observed values and change from baseline of each of the clinical laboratory results by treatment and visit. Shift tables describing abnormality shifts from baseline to after treatment and follow-up (Day 28) will be created.

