8.2.4 During Treatment Period (Day 3 and EOT, and when clinically indicated)

- Document concomitant drugs, including drug name, dose, and frequency
- Perform physical examination including respiratory exam
- Obtain chest x-ray on Day 3, in the event of clinical improvement, and at EOT, and when clinically indicated
- 12-lead ECG
- Laboratory tests including hematology, biochemistry, coagulation, and urinalysis on Day 3, EOT, and if clinically indicated
- Measure vital signs, including blood pressure (sitting), pulse rate, body temperature, respiration rate, and actual body weight (kg) daily or as clinically indicated – note: no need to document height.
- Calculate eGFR
- Administer IV drug over 2 hours
- Collect blood samples (5 mL each) at mid-point and end of the 2-hour drug infusion for PK and biomarker analysis. Prepare the samples per Section 7.3.2.2.
- Review and record any TEAEs
- Swab nasal, throat, sputum, or lower respiratory tract source for SARS-CoV-2 on Days 4, 7, 10, and 14 (if necessary).
- Complete the (1) Berlin Definition (Appendix 3), (2) SOFA score (Appendix 4), and (3) modified Medical Research Council Dyspnea Scale (Appendix 5), and (4) APACHE II score (Appendix 6; only if clinically indicated).

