10.2 Reporting of Results

The electronic Case Report Form (eCRF) is an integral part of the study and subsequent reports. The eCRF must be used to capture all study data recorded in the patient's medical record. The eCRF must be kept current to reflect patient status during the course of the study.

The monitor is responsible for performing on-site monitoring at regular intervals throughout the study to verify adherence to the protocol; verify adherence to local regulations on the conduct of clinical research; and ensure completeness, accuracy, and consistency of the data entered in the eCRF.

Arch Biopartners or its designate will monitor completed eCRFs. An eCRF will also be completed for each screened patient.

All protocol-required information collected during the study must be entered by the PI, or designated representative, in the eCRF, an internet-based electronic data collection system. All details of the eCRF completion and correction will be explained to the PI and his staff. The management module of the eCRF includes edit check and query systems that seamlessly integrate with the data entry system. All modifications to the data in the eCRF are tracked by an electronic audit trail (date and identity of the person making the change are instantaneously recorded). The eCRF will be 21CFR Part 11 compliant.

If the PI authorizes other persons to make entries in the eCRF, the names, positions, and signatures of these persons must be supplied to the Sponsor.

The PI, or designated representative, should complete the eCRF as soon as possible after data are collected, preferably on the same day that a study patient is seen for an examination, treatment, or any other study procedure. Any outstanding entries must be completed immediately after the final examination. By design, an explanation must be provided for all missing data, altered data, and/or out of range data.

The completed eCRF must be reviewed and signed by the PI named in the study protocol or by a designated sub-Investigator.

Final monitored and audited eCRFs will be provided by the Sponsor to the sites at the end of the study in the format of a PDF file.

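### Laboratory shift tables in 9.3.4.2 stop at 'after treatment' and Day 28, so on-treatment abnormalities that settle by EOT can go untabulated; add a worst on-treatment shift

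*Combined protocol and SAP*

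**What the plan says.** Section 9.3.4.2 names two laboratory outputs. The first is descriptive statistics, observed and change from baseline, for "each of the clinical laboratory results by treatment and visit". The second is the shift analysis: "Shift tables describing abnormality shifts from baseline to after treatment and follow-up (Day 28) will be created". The synopsis adds that laboratory data will be described over time and that shifts will use low, normal and high categories. It gives no time point for the shifts and names no worst value.

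The on-treatment schedule is short. Section 7.3.2.1 takes samples at Screening and then "prior to the drug infusion on Days 3, EOT, and at EOS, and as clinically indicated". The flow chart in 8.1 (footnote d) and Section 8.2.4 agree; the latter lists "Laboratory tests including hematology, biochemistry, coagulation, and urinalysis on Day 3, EOT, and if clinically indicated". EOT is tied to the last dose (8.2.5), so its day varies by patient up to Day 14.

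A worst-case rule does appear, but in the adverse event section. In the severity and attribution summaries of 9.3.4.1, "the most extreme outcome (highest severity and closest to study drug related) will be used for those patients who experience the same AE" more than once. Section 9.3.4.2, which follows it, has no counterpart for laboratory values. Section 9.3 leaves the full description of analyses to a separate SAP, to be final before database lock and unblinding.

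**The concern.** A shift table that compares baseline with the end of treatment shows who finished abnormal. It does not show who became abnormal on the way and recovered. In an acutely ill population a drug effect on liver enzymes, creatinine, platelets or clotting could be transient, and clinically indicated tests would be the likeliest place to see it. The plan expects such tests but does not say how they are tabulated.

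Clinical laboratory tests are a named safety endpoint (4.2.5), and the sample size of 60 rests partly on assessing safety in a limited number of patients (9.1). The human repeat dosing reported in 3.3.5 is 3 consecutive days, while this trial doses for up to 14 days. The 14-day rat and dog studies support that duration, but human laboratory data after Day 3 are largely new, and those collected should count in the comparison between arms. No efficacy result, error rate or stopping rule depends on this point.

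**Working it through.** The plan states no figure here, so the check is a reading of the text plus a count of days.

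**Where each result goes**, reading 'after treatment' as EOT:

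| Laboratory result | By-visit statistics (9.3.4.2) | Shift table (9.3.4.2) | Adverse event tables (7.3.1, 9.3.4.1) |
|---|---|---|---|
| Scheduled Day 3 | Yes | No | Only if judged clinically significant |
| Clinically indicated, Day 4 to the day before EOT | Not required | No | Only if judged clinically significant |
| Scheduled EOT | Yes | Yes | Only if judged clinically significant |
| Scheduled Day 28 (EOS) | Yes | Yes | Only if judged clinically significant |

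The first two rows are the gap, and they differ. A Day 3 abnormality enters the group statistics (mean, median, SD, minimum, maximum under 9.3) but is not counted as a patient moving from normal to low or high. A later clinically indicated result has no assured place in either output, because no text assigns it to a visit.

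**What the Day 3 draw covers.** It precedes that day's infusion (7.3.2.1). With once-daily dosing from Day 1, it follows at most two doses (Days 1 and 2). Among scheduled draws, only EOT reflects later on-treatment exposure.

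**Length of the window.** Days strictly between Day 3 and an EOT on Day E number E − 3 − 1 = E − 4.

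- E = 14, the maximum: 14 − 4 = 10 days (Days 4 to 13), with 2 scheduled on-treatment draws (Day 3 and Day 14).
- E = 10, assumed: 10 − 4 = 6 days.
- E = 7, assumed: 7 − 4 = 3 days.

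These are days without a scheduled draw. They do not estimate abnormalities lost: the documents do not say how many clinically indicated tests are expected or how many would be abnormal.

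**Are the data captured?** Section 10.2 says the eCRF "must be used to capture all study data recorded in the" patient's medical record, which by its general wording includes these results. Section 7.3 requires repeats of abnormal findings to be recorded. The instruction is less explicit than for imaging, however. Flow chart footnote h tells sites to record clinically warranted chest x-rays in the eCRF; footnote d, on laboratory tests, does not.

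**The case against.** The strongest reply is that this is detail for the SAP. Section 9.3.4.2 is an outline, Section 9.3 promises a SAP describing all analyses, and nothing forbids a worst-value table. That stands as a limit: the gap is in the protocol text, and the final tables may not have it.

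The wording can also be read more broadly. Section 9.3.4.2 opens by distinguishing tests before treatment from tests during it, so 'after treatment' could mean any time after treatment starts. The visit heading in 8.2.4, "During Treatment Period (Day 3 and EOT, and when clinically indicated"), could also bring clinically indicated results into the by-visit tables. Both readings are possible and neither is required by the text, which is a reason to define the term.

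The important cases are largely covered. Abnormalities that the investigator judges clinically significant must be recorded as adverse events (7.3.1), are summarised at highest severity (9.3.4.1) and are open to regular DSMB review (9.3.6). The SOFA score, which uses platelets, bilirubin and creatinine, is also obtained when clinically indicated, although it is not a laboratory shift table. A reader might infer that ten days of laboratory safety data go unreported, or that harmful abnormalities would escape notice. The documents do not support either inference.

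The contrast between 3 and 14 days of dosing might be taken as a case for more frequent sampling. That is a separate question, and no extra draws are proposed here.

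Finally, a worst-of-all-results table is sensitive to how often patients are sampled, and fixed-visit shifts avoid this. That stands, so the new table should supplement the by-visit tables and remain descriptive.

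**Conclusion.** The point holds as a modest gap in the laboratory tables and is worth considering. If 'after treatment' means EOT, shift tables miss on-treatment abnormalities that settle by EOT. Those seen on Day 3 appear only in by-visit statistics, and those seen in clinically indicated tests between Day 3 and EOT need not appear in any laboratory table. What is lost is limited to abnormalities not judged clinically significant. A comparison of counts by arm could still be informative there, since changes that look unremarkable one patient at a time can form a pattern.

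The size of the loss cannot be estimated. The 10-day window is the maximum, for a full 14-day course. The conclusion rests on the EOT reading and on the separate SAP not already providing a worst-value table; that SAP is not part of the text reviewed.

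**What to change.** In 9.3.4.2, or in the SAP before unblinding:

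- Define 'after treatment' as the EOT draw.
- Add, by arm on the Safety Population, a descriptive shift table from baseline to the worst on-treatment value of each laboratory parameter. Cover first dose to EOT, show low and high directions separately, and use all scheduled and unscheduled results captured in the eCRF.
- Show the number of results per patient alongside.
- Confirm to sites that clinically indicated laboratory results are entered in the eCRF, as footnote h already does for x-rays.
- Keep the by-visit tables for scheduled draws.

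The cost is one extra shift table per laboratory panel and one rule for unscheduled values. No extra blood draws are needed. No extra data entry is needed either if sites already apply 10.2 to these results; if not, the confirmation adds some. Sample size, error rates and efficacy analyses are unchanged. The drawback is uneven sampling: sicker patients are tested more often and frequency may differ by arm, so the table should carry no formal test and be read with the counts of results.
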